#### 7.5.2.2 Changes in QT interval

If, at any visit, a QTcF > 480 msec is seen in patients receiving pasireotide LAR, the following actions will be taken:

- A visit to a cardiologist must be scheduled as soon as possible, but within no more than 7 days of the initial abnormal ECG, and the cardiologist must re-evaluate the ECG (this can be done by the central cardiologist, if the study has one).
  - o If a QTcF > 480 msec is NOT confirmed, no action will be taken.
  - o If a QTcF > 480 msec is confirmed, a cardiologist must perform a thorough examination (such as review of baseline ECG, concurrent medication, and performance of a cardiovascular examination (including, at least, one cardiac auscultation)) in order to evaluate the patient for cardiovascular risk factors.
  - o If, based on the cardiologist's evaluation, the investigator considers that there is an acute cardiovascular safety risk and that the patient should not continue to receive the study drug, or the patient meets any discontinuation criteria (section 6.4.5.1), he/she must be immediately discontinued.

- If, after the cardiologist's examination, the investigator considers that there is no acute cardiovascular safety risk and that the patient may continue to receive the study drug, then, the following actions must be taken:
- Scenario A (Figure 7-1): If the initial ECG was performed before the pasireotide LAR injection:

A (24-hour) Holter ECG must be recorded as soon as possible, but within no more than 7 days of the initial abnormal ECG. The cardiologist evaluates the Holter ECG and provides the investigator with recommendations. The investigator analyzes the results and the cardiologist's recommendations. If a patient meets the discontinuation criteria (section 6.4.5.1), he/she will be immediately discontinued.

[figure not shown]
If a patient does not meet the discontinuation criteria, the next pasireotide LAR dose may be administered. A second Holter ECG must be recorded on the day of the next pasireotide LAR injection, and it must be started 30 min before the study drug injection. ECG, cardiac examination, and Holter ECG results, as well as the cardiologist's recommendation, must be evaluated by the investigator in order to determine whether the patient may or may not continue in the study (discontinuation criteria to be followed, Section 6.4.4 and Section 6.4.5).

If an abnormal ECG is seen on Visit 10 and no additional dose of pasireotide LAR is administered, then the follow-up is at the investigator's discretion.

Scenario B (Figure 7-2): If the initial ECG is performed at Visit 3 (Day 20) or at Visit 6 (Day 76):

[figure not shown]
A (24-hour) Holter ECG must be recorded as soon as possible, but within 7 days of the initial abnormal ECG. The cardiologist evaluates the Holter ECG and provides the investigator with recommendations. The investigator analyzes the results and the cardiologist's recommendations. If a patient meets the discontinuation criteria (Section 6.4.4 and Section 6.4.5), he/she will be immediately discontinued. If the investigator decides that the patient may continue in the study, he/she will be invited to return to the next regular visit, according to the visits and evaluations schedule (Table 7-1).

Figure 7-1 Scenario A: Procedure for QTcF Prolongations Occurring on the Planned Pasireotide LAR Dosing Visits

Visit 10: If QTcF > 480 msec on this visit and no additional pasireotide LAR dose is administered, then the follow-up is at the investigator's discretion.

Figure 7-2 Scenario B: Procedure for QTcF Prolongations Occurring on visits 3 and 6 Planned Only for Patients Receiving Pasireotide LAR

#### 7.5.2.3 Liver safety monitoring

If any of the criteria below is observed on any scheduled or unscheduled visit, the sponsor must be informed as soon as the occurrence is acknowledged.

- ALT or AST > 3 x ULN and Total Bilirubin  $\ge 2$  x ULN
- ALT or AST > 5 x ULN and  $\le 8$  x ULN
- ALT or AST > 8 x ULN

The following tests will be performed immediately within **72 hours** after the abnormality is acknowledged:

• Perform liver-oriented medical history and physical examination (i.e., evaluate occupational risks, concurrent medication, including over-the-counter medication, concurrent disease, etc.)

- Liver tests: ALT, AST, total bilirubin (bilirubin fractionated in direct / indirect, if total bilirubin is > 2.0 x ULN), Albumin, PT (INR), ALP, and  $\gamma$ -GT
- Perform hepatitis tests: anti-HAV IgM (to confirm acute Hepatitis A), HBsAg, anti-HBc, anti-HCV (if positive, viral load PCR must be evaluated), anti-HEV, ANA antibodies, anti-smooth muscle antibodies, CMV and EBV
- Perform abdominal ultrasound (liver and bile duct)
- Collect pharmacokinetic samples and record the level and time of the last dose the patient received before the pharmacokinetic sample.

Liver function tests must be monitored every **3 - 4 days** until resolution or return to baseline level.

[figure not shown]
Patients may need to be discontinued if the abnormal liver function criteria are met when the liver tests are repeated (refer to discontinuation criteria on Section 6.6.5.1). The reports of the course of the event must be kept until resolution or stabilization (i.e., no elevation after 2 consecutive evaluations).

For ALT or AST > 5 x ULN and  $\le 8$  x ULN, the following must occur (in addition to the safety follow-up procedures listed above):

- The study medication must be temporarily interrupted and the liver tests monitored every **3 4 days** until resolution or return to baseline level.
- If no resolution or return to baseline occurs after 2 weeks, the patient must be discontinued.
- If ALT or AST return to less than 5 x ULN, the study medication may be resumed and the patient may continue the study according to the protocol.
- If ALT or AST increase to over 5 x ULN at any time after the study medication is resumed, then the study medication must be immediately discontinued.

If any of these criteria is met and considered as an adverse event by the investigator, the event must be recorded on the Adverse Event page of the case report form; if the event is considered severe by the investigator, then proceed to complete the SAE form. Additionally, any significant finding of the physical examination must be recorded in the Adverse Event page of the case report form.

Figure 7-3 Liver Test Monitoring Algorithm

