#### 6.4.5 Early patient discontinuation

#### 6.4.5.1 End of treatment

Patients may withdraw voluntarily from the study or be withdrawn, at the investigator's discretion, at any time. They may be considered as discontinued if they declare their intention to discontinue, or if they do not return for visits, or if they are lost to follow-up for any other reason. Patients may be withdrawn from the study by the investigator for any of the following reasons:

- Acute or progressive vision loss confirmed by a new evaluation of the visual field
- Increased tumor volume defined as tumor volume growth (>20%) and confirmed in a second MRI performed approximately one month later
- Pregnancy
- Adverse event(s)
- Uncontrolled diabetes mellitus
- Clinically significant abnormal laboratory value(s)
- Clinically significant abnormal result(s) of test procedures
- Protocol violation
- Lost to follow-up
- Administrative problems
- Death
- Patients who experience:
- ALT or AST > 3 x ULN and Total Bilirubin  $\ge 2$  x ULN and ALP < 2 x ULN
- ALT or AST > 5 x ULN and  $\le 8$  x persistent ULN for more than 2 weeks
- ALT or AST > 8 x ULN

If any of the discontinuation criteria is met, the study medication must be immediately discontinued. Additionally, appropriate safety follow-up monitoring must be performed, as defined on Section 7.5.2.3. Resuming the study medication after the discontinuation criteria are met is not allowed.

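### For ALT/AST above 5 and up to 8 x ULN, Protocol 7.5.2.3 can require stopping and permit resumption in the same patient, and 6.4.5.1 uses a different two-week test

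*Protocol*

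**What the plan says.** Two sections of the protocol govern this ALT/AST band.

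**Section 7.5.2.3 (Liver safety monitoring).** For values above 5 and up to 8 x ULN, the first instruction is: "The study medication must be temporarily interrupted and the liver tests monitored every" 3 to 4 days, until resolution or return to the baseline level. Two further bullets follow: "If no resolution or return to baseline occurs after 2 weeks, the patient must be discontinued" and "If ALT or AST return to less than 5 x ULN, the study medication may be resumed". A later rise above 5 x ULN after resumption means immediate discontinuation. A more general sentence covers all three liver triggers: "Patients may need to be discontinued if the abnormal liver function criteria are met when the liver tests are repeated". It sends the reader to Section 6.6.5.1 for the criteria.

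**Section 6.4.5.1 (End of treatment).** The list opens with "Patients may be withdrawn from the study by the investigator for any of the following reasons". It mixes general reasons (adverse events, clinically significant laboratory abnormalities, loss to follow-up, death and others) with three liver thresholds. The threshold for this band reads "x persistent ULN for more than 2 weeks"; the word order is odd, but the sense is persistence in the band. After the list comes "If any of the discontinuation criteria is met, the study medication must be immediately discontinued", then a pointer to 7.5.2.3 for follow-up, then a statement that study medication may not be restarted once the criteria have been met.

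**The concern.** Amendment 2 was written to add liver safety measures, so these are the rules a site will consult when a liver result comes back abnormal. Two of the 7.5.2.3 bullets use different end points. The mandatory stop depends on resolution or baseline at two weeks, while permission to resume depends on being below 5 x ULN at no stated time. Any value between the two end points at two weeks satisfies both bullets. Section 6.4.5.1 then applies a third condition at about the same time. Two investigators with the same laboratory series could reach opposite decisions on re-exposure, and each could cite the protocol.

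The dosing interval makes this a practical question. Liver tests fall on Day 20 (Visit 3) and the second injection on Day 28 (Visit 4). Take an illustrative patient at 6 x ULN on Day 20 and 4 x ULN on Day 28. The resumption bullet permits the Day 28 injection. Two weeks after onset is Day 20 + 14 = Day 34. If the patient is still above baseline then, the other bullet requires discontinuation six days after a depot dose intended to cover 28 days.

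**Working it through.** The plan has no figure to reproduce here. The check is to apply the rules as written to a few ALT courses and list which instructions each one triggers.

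**Inputs from the protocol**
- 7.5.2.3 stop: no resolution or return to baseline after two weeks.
- 7.5.2.3 resumption: value below 5 x ULN, with no time limit and no link to the stop bullet.
- 6.4.5.1 liver criterion: above 5 and up to 8 x ULN for more than two weeks; restarting is then barred.

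**Assumptions.** The ALT values are illustrative. The protocol gives no numeric meaning for *resolution*, so it is first taken as ALT at or below the larger of baseline and 1 x ULN.

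| Course (x ULN, baseline 1) | 7.5.2.3 stop | 7.5.2.3 resumption | 6.4.5.1 criterion and ban |
|---|---|---|---|
| A: 6 at day 0, 3 at day 7, 1 from day 11 | no | yes, from day 7 | no |
| B: 6 at day 0, 4 at day 7, 3 at day 14 | **yes** | **yes**, from day 7 | no |
| C: 6 at day 0, 5.5 at day 11, 4.9 at day 14 | **yes** | **yes**, from day 14 | no |
| D: 6 through day 14, 5.5 at day 18, 4 at day 21 | yes | yes, from day 21 | yes |

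Course B gives the same result with a baseline of 2 x ULN.

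**Reading the table.** Course A has no conflict. Courses B and C meet the stop bullet and the resumption bullet together, while the 6.4.5.1 liver criterion is not met. Course D meets the wording of all three, but there the two stopping rules agree, and only the open-ended resumption bullet points the other way.

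**Sensitivity to the undefined word.** Let t be the level at which ALT counts as resolved. The conflict covers patients whose lowest value by two weeks lies above both t and baseline but below 5 x ULN. Course B (lowest value 3) conflicts if t is below 3, and course C (lowest value 4.9) conflicts if t is below 4.9. If t means anything below 5 x ULN, both conflicts disappear. The band therefore runs from empty to the whole range between baseline or normal and 5 x ULN, according to a definition that the text does not give.

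**Cross-reference.** Section 6.6.5.1 is not in the current protocol. The criteria stand in 6.4.5.1.

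**The case against.** The strongest reply is that the rules can be read as one. If *resolution* means that the trigger above 5 x ULN has cleared, then the stop bullet, the resumption bullet and the persistence test in 6.4.5.1 fit together. That reading is coherent, and the sponsor may have meant it. But the text does not state it. Section 7.5.2.3 gives below 5 x ULN as a separate threshold, and it uses resolution or return to baseline as the end point for testing every 3 to 4 days. On the harmonised reading, close monitoring could end at 4.9 x ULN. Figure 7-3, the liver algorithm, could not be consulted for this point. It may set out the sequence, but it would not remove the conflicting sentences. The sponsor must be told of every such result, which lowers the risk of divergent site decisions but does not supply the missing rule.

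A reader might infer more than the documents support:

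- **That one patient always receives all three instructions.** Courses B and C do not meet the 6.4.5.1 liver criterion, so the ban does not reach them through it. In course D, permission to resume is naturally read as resuming from the temporary pause, not after discontinuation. The ban would reach B and C only if the open item on clinically significant laboratory values were also a mandatory criterion, and the text leaves that unclear.
- **That every patient above 8 x ULN is affected.** The permissive sentence ("Patients may need to be discontinued if the abnormal liver function criteria are met when the liver tests are repeated") covers all three triggers and defers to the discontinuation criteria. For values above 8 x ULN those criteria require an immediate stop. What remains is the wrong section number.
- **That 6.4.5.1 overrides Table 6-2 for any adverse event.** The closing paragraph directly follows the liver thresholds and points to the liver section, so it is most naturally read as governing those thresholds. Its scope is still unstated, and 7.5.2.2 cites the 6.4.5.1 criteria generally, so clarification is warranted.
- **That each withdrawal removes a patient from the Week 24 denominator.** One of 19 is 1/19 = 5.3%, but the loss is not established. Section 6.4.4 schedules Visit 10 with all its evaluations 28 ± 3 days after the last dose for early stoppers, and SAP Table 7 tabulates volumes by V10. The documents do not say that such a scan is excluded.

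**Conclusion.** The point holds for the band above 5 and up to 8 x ULN. As written, Section 7.5.2.3 can both require discontinuation and permit resumption for a patient who is below 5 x ULN but neither resolved nor at baseline at two weeks. Section 6.4.5.1 applies a different two-week test, and its ban on restarting applies through the liver criterion only when values stay above 5 x ULN for more than two weeks. The dead reference and the unassigned shift from *may* to *must* in 6.4.5.1 add to the uncertainty.

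The conclusion rests on *resolution* meaning something lower than 5 x ULN, or at least on the text not excluding that. The number of patients cannot be estimated, because the documents give no expected rate of such elevations. The consequence is inconsistent handling of re-exposure after a liver signal; a bias in the primary result is not demonstrated. The passages should be reconciled because they govern patient safety and the correction is small.

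**What to change.** The sponsor's clinical team should:

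1. Reconcile 6.4.5.1 and 7.5.2.3 so that this band has one two-week test, one stated meaning of *resolution* and one resumption statement, and check Figure 7-3 against the result.
2. Replace the reference to 6.6.5.1 in 7.5.2.3 with 6.4.5.1.
3. Mark which items in the 6.4.5.1 list are mandatory and which are at the investigator's discretion, and say which of them the closing paragraph and the ban on restarting cover.

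The choice of clinical rule belongs to the clinical team, and none is proposed here. The cost is a short protocol amendment or clarification, with its ethics submission and notice to sites. It adds no visits, tests or data collection.

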# 7.5 Safety

#### 7.5.1 Adverse events

An AE for the purposes of this protocol is the onset of (or worsening of) untoward (pre-existing) sign(s), symptom(s), or clinical condition(s) occurring after signature of the Informed Consent Form, even if the event is clearly considered not related to the study drug(s). Refer to Section 6 for specific protocol definitions of study drug and study treatment.

AEs will be evaluated according to the Common Terminology Criteria for Adverse Events (CTCAE) version 4.0. If there is no CTCAE classification for an adverse event, mild, moderate, severe, and potentially fatal severities **or** grades 1 to 4 will be used. CTCAE grade 5 (death) will not be used in this study; this information will be gathered in the End of Treatment or Survival Information eCRF. AE monitoring must continue for at least 4 weeks after administration of the last dose of the study treatment.

AEs occurring before the study treatment is started, and after the Informed Consent Form is signed, are recorded in the Medical History / Current Medical Conditions electronic Case Report Form.

Abnormal laboratory values or abnormal test results only constitute AEs if they lead to clinical signs or symptoms, are considered clinically significant, or require therapy (e.g., any hematological abnormality requiring transfusion or treatment with cytokines), and must be recorded in the Adverse Events eCRF according to associated signs, symptoms, or diagnoses. Additionally, single abnormal laboratory values that are considered clinically significant (for example, causing study discontinuation or constituting, themselves, a serious adverse event) must be recorded in the Adverse Events eCRF. SAEs occurring after the Informed Consent Form is signed are recorded in the Adverse Event eCRF.

The occurrence of AEs must be obtained by means of indirect questioning to the patient on every visit throughout the study. AEs may also be detected when voluntarily reported by the patient during or between visits or through physical examination, laboratory tests, or other evaluations. Whenever possible, each AE must be evaluated to determine:

- 1. Severity grade (CTCAE grade 1 4)
- 2. Relationship to pasireotide LAR (suspected / non-suspected)
- 3. Duration (onset and end dates or if ongoing at the final examination)

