- 4. Action taken (no action taken; study drug dose adjusted / temporarily interrupted; study drug permanently discontinued due to this AE; concurrent medication administered; non-drug therapy administered; hospitalization / prolonged hospitalization)
- 5. If serious, a serious adverse event (SAE) is defined as an event that:

- Is fatal or potentially fatal
- Results in persistent or significant disability / incapacity
- Constitutes a congenital anomaly / birth defect
- Requires hospitalization or prolongation of ongoing hospitalization, unless the hospitalization is for:
  - Routine treatment or monitoring of the indication studied; not associated to any condition deterioration (specify what this includes)
  - Elective or pre-planned treatment to a pre-existing condition that is not related to the study indication and did not worsen since the consent form was signed
  - Emergency outpatient treatment for an event that does not meet any of the SAE definitions provided above and does not result in hospitalization
  - Social reasons and temporary care in the absence of any deterioration of the general patient condition
- Is clinically significant, i.e., defined as an event that puts the patient at risk or that might require medical or surgical intervention to prevent one of the results listed above

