#### 7.5.2.4 Gadolinium

There are known adverse events after the use of Gadolinium as contrast material in MRI scans. Caution must be taken with patients with current and previous renal failure.

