# 8 Safety monitoring

# 8.1 Serious adverse event reporting

In order to ensure patient safety, each SAE, **regardless of the suspected causality**, occurring after the beginning of any period in which the study protocol interferes with the standard medical care given to the patient (for example, withdrawal of treatment during washout period, change in treatment for a fixed dose of concurrent drug) and up to 56 days after the patient receives the last IM LAR injection of the study drug must be reported to Novartis within 24 hours after acknowledgement. Any SAE experienced after this period must be reported to Novartis if the investigator suspects that there is a causal relationship to the study drug. Recurrent episodes, complications, or progression of the initial SAE must be reported as a follow-up to the original episode within 24 hours of receipt of the follow-up information by the investigator. A SAE occurring in a different timepoint or considered as not otherwise related to a previously reported event, must be reported separately as a new event.

The information about all SAEs is collected and recorded in the Serious Adverse Event Report Form. The investigator must evaluate and register the relationship between each SAE and each specific study drug (if there is more than one study drug), complete the SAE Report Form in English, and fax it, completed and signed, within 24 hours to the Novartis Integrated Medical Safety (IMS) Oncology Department.

The site-specific phone and fax numbers of the contact people at the local IMS department are indicated in the investigator's binder provided to each site. The original copy of the SAE Report Form and the fax confirmation page must be kept together with the documentation of the case report form at the study site.

Follow-up information is submitted to the same person as the original SAE Report Form, using a new SAE Report Form, indicating that this is a follow-up of a previously reported SAE and mentioning the date of the original report. Each recurrence, complication, or progression of the original event must be reported as a follow-up to that event, regardless of when it occurs. Follow-up information must describe whether the event resolved or continues, whether and how it was treated, whether there was unblinding or not, and whether the patient continued or discontinued his/her participation in the study.

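### Section 7.5.2.3 sends liver events to the SAE form on severity rather than seriousness, and Section 8.1 gives 24-hour SAE reporting no study-specific start

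*Protocol*

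**What the plan says.** **SAE trigger for liver events.** Protocol Section 7.5.2.3 applies when one of its transaminase or bilirubin criteria is met and the investigator regards the finding as an adverse event. The event is then entered on the adverse event page and, "if the event is considered severe by the investigator, then proceed to complete the SAE form".

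**SAE definition.** Section 7.5.1 lists severity (CTCAE grades 1 to 4) as the first attribute to record for an adverse event. Where no CTCAE grade exists it supplies a substitute scale: "If there is no CTCAE classification for an adverse event, mild, moderate, severe, and potentially fatal severities". Seriousness comes later in the same list and is introduced by "If serious, a serious adverse event (SAE) is defined as an event that". The outcomes that follow are a fatal or potentially fatal event, disability, congenital anomaly, hospitalisation, and a final limb: "Is clinically significant, i.e., defined as an event that puts the patient at risk or that might require medical or surgical intervention". The intervention meant there is one that averts another outcome on the list. Being severe is not among them.

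**Start of recording and of reporting.** Section 7.5.1 states: "SAEs occurring after the Informed Consent Form is signed are recorded in the Adverse Event eCRF". Section 8.1 requires 24-hour reporting of SAEs "occurring after the beginning of any period in which the study protocol interferes with the standard medical care given to the patient" and up to 56 days after the last injection. Its examples are a washout and a switch to a fixed dose of a concurrent drug.

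**The concern.** Severity and seriousness are different attributes, and Section 7.5.1 treats them as different. Using one as the trigger for the other means that the liver section and the general safety section can classify the same event differently. Liver safety is what Protocol Amendment 2 was written to address, so this is the part of the safety plan where routing most needs to be clear.

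The second issue is the reporting window. Screening runs from Day -28 to Day -1 and includes an MRI with gadolinium. Section 7.5.2.4 acknowledges that "There are known adverse events after the use of Gadolinium as contrast material in MRI scans". If sites read the start of Section 8.1 differently, an SAE in screening could be recorded in the eCRF at one site without being expedited, and expedited at another.

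**Working it through.** The plan states no figure on this point, so there is nothing to reproduce. The check sets the texts side by side.

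**Step 1. Cross-classify liver events that meet a Section 7.5.2.3 criterion and are judged adverse events.**

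| Event | Section 7.5.2.3 | Sections 7.5.1 and 8.1 | Agree? |
|---|---|---|---|
| Severe and serious | SAE form | SAE | Yes |
| Severe, not serious | SAE form | Adverse event only | No |
| Serious, not severe | Not sent to the SAE form by this section | SAE, 24-hour report | Silent, but covered by 8.1 |
| Neither | No SAE form | Adverse event only | Yes |

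**Step 2. Can an event be severe and not serious?** The protocol's own text allows it. Section 6.4.5.1 lists ALT or AST above 8 x ULN as a discontinuation criterion. Section 7.5.1 says that a single clinically significant laboratory value is recorded as an adverse event. It gives two alternative examples: a value that causes discontinuation, and a value that is itself an SAE. If every value causing discontinuation were an SAE, the second example would be redundant. An asymptomatic elevation graded severe can therefore be a non-serious adverse event under 7.5.1 and still go to the SAE form under 7.5.2.3.

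**Step 3. Is the serious, non-severe event lost?** Two provisions limit that. Section 8.1 applies to each SAE in its window whatever its suspected cause, and nothing in 7.5.2.3 suspends it. Section 7.5.2.3 also requires the sponsor to be informed as soon as any of its three criteria is seen, without reference to severity or seriousness.

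**Step 4. Does over-routing reach the tables?** SAP Tables 15, 17, 19, 21 and 23, and extension Tables B 9, B 11, B 13, B 15 and B 17, report serious events. SAP Section 5.5.3.1 does not say that the expedited form is their source. A misrouted event inflates them only if it is also flagged serious in the analysed data.

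**Step 5. Does the start of Section 8.1 affect the tables?** SAP Section 5.5.3.1 counts as treatment-emergent those events that start between the first administration and 28 days after the last. An SAE before first dose lies outside that definition wherever 24-hour reporting begins. The effect on the core treatment-emergent tables is 0.

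**Step 6. Weight of one patient (illustration).** Assume that all 23 planned patients are in the safety set. The change in the patient-level SAE percentage is k/23 for k patients wrongly classed:

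- k = 1: 1/23 = 4.3 points
- k = 2: 2/23 = 8.7 points
- k = 3: 3/23 = 13.0 points

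This applies where the denominator is patients: the patient row of Table 15, Table 17 and, for suspected relationship, Table 19. Tables 21 and 23 use the number of serious events as denominator, which is unknown in advance.

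**The case against.** The best reply is that the consequences are small and the wording may be accidental. Much of that stands.

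- **Breadth of the definition.** The clinically significant limb in 7.5.1 is wide, and some severe liver events would qualify as SAEs under it. This narrows the mismatch without removing it, as Step 2 shows.
- **Translation.** The trial is run in Brazil and the English reads as a translation, so *severe* may stand for *serious*. That is an inference, since the site-language text is not available here. The liver algorithm in Figure 7-3 is not shown either. If it is a slip, the text still needs correcting.
- **Reporting window.** The washout in 8.1 is only an example. A protocol-required contrast MRI can reasonably be read as interfering with standard care, which would bring it inside the window. What remains is that no visit or date is named, and that the example does not fit treatment-naive patients with no described washout. For patients who never start treatment, Sections 6.2 and 7.1 mention only the Screening Record and Demographics eCRFs, which does not help.

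A reader might go further and infer that SAE counts will be wrong, or that serious liver events will go unreported. The documents do not support either. Completing an SAE form is not the same as being counted serious in a table. Section 8.1 and the sponsor notification cover the serious but non-severe case, and screening events cannot enter the treatment-emergent tables.

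**Conclusion.** The liver section uses the wrong trigger for the SAE form when measured against the protocol's own definition. The supported consequence is that liver events may be classified inconsistently, with over-classification the likelier direction. Secondarily, the start of 24-hour reporting is not tied to any event in this study and does not match the consent-based start in 7.5.1. That affects expedited reporting in screening and nothing in the treatment-emergent tables.

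The size of any error cannot be estimated, because the documents give no rate of severe but non-serious liver events or of pre-dose SAEs. The 4.3 points is the weight of one patient under an assumed safety set of 23 and should not be read as an expected bias. The primary endpoint is unaffected.

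**What to change.** 1. In Section 7.5.2.3, replace *severe* with *serious (as defined in Section 7.5.1)* and cross-refer to Section 8.1. Check that Figure 7-3 and the site-language text use the same trigger.
2. In Section 8.1, state one explicit start point for SAE reporting, signature of the informed consent form, to match Section 7.5.1. Delete the washout example.

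The cost is two wording changes in an amendment and a memo to sites. There may be a few more SAE reports from screening. No new procedures or data are needed.
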